## DEFINITION OF TERMS

Term	Source	Definition
Calendar days	NAOB	Every day on the calendar, including weekends and public holidays.
Disability pension	NAV	Regular income to individuals who are unable to work due to a permanent disability. To be eligible for disability pension, the illness and/or injury must be the main cause of reduced work and earning capacity.
Employment	ILO/WHO	An agreement to produce goods or services for a specific period in time for compensation by a salary, a wage or in kind. Different types of employment exist, among which is self-employment.
Part-time employment	ILO/WHO	When the hours of work are less than the 'normal' hours of work of comparable full-time employment.
Prolonged sickness absence	[1–5]	Sick leave for >90 continuous days or >180 continuous days
Sick leave/sickness absence/work absence	EULAR	Time off from work that workers can use to stay home to address their health and safety needs without losing pay.
Work assessment allowance	NAV	Financial support provided by the government for people who are unable to work due to illness or injury, but are expected to return to work in the near future.
Work disability	ILO	When an individual is unable to perform work-related tasks due to physical or mental impairments or disability.
Workdays	NAOB	Any of those days of a week on which work is done, officially Monday to Friday, a 5-day workweek.

Abbreviations: EULAR, European Alliance of Associations for Rheumatology; ILO, International Labour Organisation; NAOB, Norwegian Academy Dictionary; NAV, Norwegian Labour and Welfare Service; WHO, World Health Organization.

## BACKGROUND

Long-term sickness absence due to musculoskeletal disorders (MSDs) is associated with substantial societal costs, constituting a major concern for the welfare state in western societies [6]. In Norway, the sickness absence rate is among the highest in Northern Europe and MSDs accounted for 35-39% of the total sickness absence [7]. Although it is only a small proportion of individuals that experience long-term sick leave, this group is responsible for the majority of the total sick leave cost [6]. Early identification of workers on sick leave at risk of prolonged work absence is therefore important to guide stratified prevention strategies to improve individual outcomes and reduce societal costs [8]. This targeting can be done by using prognostic models [9].

There have been some previous attempts to develop prognostic regression models for predicting work absence. However, most of these models were either developed for individuals without an employment contract or for workers not already on sick leave, aiming at primary prevention strategies [4,10–15]. Of the few prognostic models developed for secondary prevention, the models have either demonstrated insufficient performance, lack external validation [14,16], have been developed in a homogenous sample with a specific diagnosis [4], or in a specific work sector [17]. Thus, a crucial need exists for accurate models to predict risk of long-term, or prolonged, sickness absence used within the earlier stage of an MSD-related sick leave.

To address this, we aim to develop and externally validate prognostic models to predict an individual's risk of prolonged sickness absence due to MSDs in a social insurance setting in Norway. However, the definition of prolonged or long-term work absence outcomes can vary greatly, with most previous prognosis studies using anything from over 14 days to over 365 days [2,10,18,19]. In this study, we have defined three binary outcomes for prolonged sickness absence: (1) being on sick leave for more than 90 consecutive days, (2) more than 180 consecutive days, and (3) any new episode or increase in work assessment allowance (WAA) and/or disability pension (DP) during a 1-year follow-up [1–5]. Therefore, we need to develop three separate prognostic models for each outcome.

## Objectives

Our study objectives are to:

1. Develop and internally validate three prognostic models for prolonged sickness absence (>90 consecutive days, >180 consecutive days, and granted WAA/DP) used within the first 4-12 weeks of sick leave due to an MSD in a social insurance setting.
2. Externally validate these models and assess their clinical usefulness in a new sample separate from the sample used in the development stage.

## METHODS

Our study design will be informed by the PROGRESS framework [9] and will be reported according to the Transparent Reporting of a multivariable prediction model for Individual Prognosis Or Diagnosis (TRIPOD) statement for prediction studies [20,21].

### Data sources

This study involves analysis of data from three data sources: a cohort study and two randomised controlled trials (RCTs). All three studies collected 12 months of sick leave data from participants. We will use all arms of the RCTs (intervention and control groups). The study protocols and details of these studies have been published elsewhere [22–24], and detail on study populations is briefly described below and in Table 1.

#### *Development sample*

To develop the models, we will combine data from a prospective cohort study [22] and an RCT (MI-NAV trial) [25]. The prospective cohort study was carried out from November 2018 to February 2020, involving workers on sick leave due to MSDs who were invited to participate through the electronic communication website of the Norwegian Labour and Welfare Service (NAV). The inclusion criteria were workers aged 18 to 67 years on sick leave for a minimum of 4 weeks with a diagnosis within the musculoskeletal (L) chapter of ICPC-2 (International Classification of Primary Care, Second edition) [26]. Exclusion criteria were insufficient Norwegian or English

language skills to participate in the study. This study recruited 549 participants with median age of 50.1 (interquartile range [IQR], 41.9-56.9) years, who had been on sick leave at a median of 37.8 (IQR, 26.1-80.3) workdays the year prior to the baseline assessment.

The MI-NAV trial was a multi-arm randomised controlled trial investigating the effectiveness of adding motivational interviewing or stratified vocational care intervention to usual care in a sample of workers on sick leave due to MSDs. The inclusion criteria in this trial were similar to the prospective cohort study: participants were eligible if they were aged 18-67 years, employed full or part-time, and on sick leave due to MSDs (L-chapter of ICPC-2) for at least 50% of their contracted work hours for more than 7 weeks. Exclusion criteria included serious somatic or mental health disorders, pregnant women, those who were unemployed, freelancers, self-employed workers and people lacking sufficient Norwegian or English language skills. This trial consisted of 514 participants, median age 48.8 (IQR, 40.8-55.3) years, who had been on sick leave at a median of 36.8 (IQR, 29.3-50.0) workdays the year prior to the baseline assessment. The MI-NAV trial showed a 7-day non-statistically significant reduction in sickness absence over 6 months for the intervention groups compared to usual care.

**Table 1.** Characteristics of the datasets that will be used in this study.

Study	N	Study type	County, Country	Diagnosis coding	Follow-up time	Inclusion criteria	Linkage to sickness absence registry data	Intended use of database
Prospective cohort study [22]	549	Prospective cohort	All counties, Norway	ICPC-2	12 months	Sick leave due to MSD for at least 4 weeks. Aged 18-67 years.	Yes	Development
MI-NAV trial [25,27]	514	Three-arm parallel RCT	Vestfold, Norway	ICPC-2	12 months	Sick leave due to MSD for at least 7 weeks (>50 % of contracted working hours). Aged 18-67 years.	Yes	Development
MI study [24]	865	Three-arm parallel RCT	Trøndelag, Norway	ICPC-2	12 months	Sick leave due to any diagnoses for at least 8 weeks (>50 % of contracted working hours). Aged 18-60 years.	Yes	External validation

Abbreviations: ICPC-2, International Classification of Primary Care 2nd version; MI, motivational interviewing; MSD, musculoskeletal disorders; RCT, randomised controlled trial.

### *Validation sample*

We will externally validate the models using data from all arms of a second RCT (MI study) [24]. This study evaluated the effect of motivational interviewing on return to work in a social security setting using a parallel group design. Participants aged 18 to 60 who had been on sick leave for more than 8 weeks were recruited through the NAV system. Individuals who were not employed or pregnant were excluded. This trial comprised 865 participants, median age 45.0 (IQR, 37.0-52.0) years, who had been on sick leave at a median of 52.1 (IQR, 40.4-65.6) workdays the previous year. The results from this trial have not been published yet.

The inclusion criteria for all studies are pragmatic and unrestricted, indicating that they are likely to be representative of the target population. We plan to use data from all arms (intervention and control) of the RCTs.

### **Source population**

Our prognostic models will be focused on information collected between the initial 4-12 weeks of a sick leave spell due to MSDs. As such, participants of each dataset will be eligible if they at baseline were:

- On sick leave due to a musculoskeletal diagnosis within the musculoskeletal (L) chapter of ICPC-2 [26].
- On sick leave for at least 50% of their contracted work hours for 4-12 consecutive weeks.

Individuals on sick leave for more than 12 weeks at baseline were excluded.

### **Setting**

All data sources are from a social insurance setting in Norway.

### **Sickness absence data**

Sickness absence days will be measured using registry data from the National Social Security System Registry where all individuals receiving any form of benefits in Norway

are registered by their social security number. We will extract sick leave data for each participant from 12 months before and 12 months after baseline.

In Norway, after 12 months of sick leave, it is possible to apply for long-term medical benefits: work assessment allowance, and disability pension. Both provide approximately 66% of the income and can be granted for 20-100% of ordinary working hours. Disability pension can be combined with part-time work. Therefore, a person receiving disability pension can also be on part-time sick leave.

In this study, we will calculate days of medical benefits according to a 7-day week for every month during follow-up. Days on sick leave will be adjusted for part-time sick leave, work assessment allowance, and disability pension. Any new episode or increase in disability pension during follow-up will be counted as sick leave. Furthermore, we will adjust days on sick leave based on the participant's contracted working hours. For example, a person who works part-time at 50% and is 100% on sick leave will have 3.5 calendar days of sick leave during a week.

### **Start-point (time of prediction)**

The start-point, the time of intended prediction, will be within the initial 4-12 weeks of sick leave due to an MSD.

We chose this time window (within 4-12 weeks) based on two aspects. Firstly, the majority of workers on sick leave with MSDs will return to work within the first 4 weeks [5], and we therefore believe that it is not beneficial to screen all individuals within their first weeks on sick leave. Secondly, it is important not to wait too long with intervention strategies, as the longer people are away from work the less likely they are to return [28,29]. This time window is in line with recommendations for when work disability prevention strategies should be initiated [30–32].

### **End-points (outcome definitions)**

The end-points (outcomes) to be predicted are three binary end-points that characterise prolonged sickness absence during the follow-up of 12 months:

1. Over 90 days of work absence during the first sick leave spell, defined as the number of calendar days during a continuous episode of full-time or part-time sick leave. Coded as 0 = ' $\leq$ 90 days', 1 = ' $>$ 90 days'.
2. Over 180 days of work absence during the first sick leave spell, defined as the number of calendar days during a continuous episode of full-time or part-time sick leave. Coded as 0 = ' $\leq$ 180 days', 1 = ' $>$ 180 days'.
3. Any new episode or increase in work assessment allowance (WAA) and/or disability pension (DP) during follow-up. Coded as 0 = 'no WAA/DP', 1 = 'new episode/increase in WAA/DP'.

For end-point 1 and 2, the end of the first sick leave spell will be censored at 'full sustainable return to work' or end of follow-up. We defined 'full sustainable return to work' as having returned to work for 4 weeks or more without benefits [24,33].

We considered a large number of end-points to capture the concept of prolonged sickness absence since the definition of prolonged or long-term sickness absence varies in different studies and no consensus exists. End-points predicted by existing prognostic models were also considered. We regarded a cut-off of 90- and 180-days to be clinically meaningful. This agrees with a recent report on sick leave in Nordic countries [5] and previous studies [2,4,34,35]. Furthermore, these end-points are in line with a recent recommendation for measuring work participation, stating that absenteeism should include sick leave duration in days [36]. However, since no consensus exists, we plan to conduct a sensitivity analysis for different end-points (see "Sensitivity analysis" section).

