Prognostic factor	Definition	Variable type	Unit/categories	Measurement method	No. of predictor parameters	Evidence
Expectation of RTW	Expectation of probability of returning to work within 3 months	Continuous	0-10, 10 = best	Self-reported using item from ÖMPSQ-SF [55]	1	[14,17,28,40,52,56–63]
Pain intensity	Pain intensity last week	Continuous	0-10, 10 = worst	Self-reported	1	[17,38,43,52,53,61–65]

Depression/ anxiety	Self-reported depression or anxiety	Categorical	Recategorized from 5 to 3 categories	Self-reported using item from EQ5D [66]	3	[10,28,43,67]
Education level	Completed education	Binary	0 'Lower education: primary/secondary/voc ational school' 1 'Higher education: College/University. Recategorized from 4 to 2 categories	Self-reported	1	[10,13,14,18,2 8,44,45,52,53, 59]
Age	Age	Continuous	Years	Self-reported	1	[4,10,14,17,18 ,28,38–40,43– 46,52,53,56,5 8–63]
Previous sick leave	Days of sick leave previous year	Continuous	Days	Register data	1	[4,10,17,18,28 ,45,46,52,53,5 6]
Disability pension status	Receiving work assessment allowance or disability pension at starting-point	Binary	0 'No' 1 'Yes'	Register data	1	[4,10,17,18,28 ,45,46,52,53,5 6]
General health	Self-perceived general health	Continuous	0-100	Self-reported using VAS from EQ5D [66]	1	[10,18,40,44,4 5,52,53,61,62]
Fear- avoidance	Fear that movement or activity will worsen the injury	Binary	0 'No' 1 'Yes'	Self-reported using item from Keele STarT MSK tool [68,69]	1	[39,40,43,53]
Workability (job performance)	Self-reported current workability compared to at its best	Continuous	0-10, 10=best	Self-reported using item from Work Ability Index [35]	1	[18,35,44,46,5 2,53]
Intervention	Participant in a trial arm with an effective intervention	Binary	0 'No' 1 'Yes'		1	[70]
					Total 13	

[figure not shown]
Abbreviations: EQ5D, Euroqol questionnaire 5-dimensions; ÖMPSQ-SF, Örebro Musculoskeletal Pain Screening Questionnaire short form; RTW, return to work; SA, sickness absence; VAS, visual analogue scale.

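### As written, the first sick-leave spell cannot close while a baseline work assessment allowance or disability pension continues, and the SAP's own day-counting rules point the other way

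*SAP*

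**What the plan says.** All references are to the prognostic-model SAP.

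- **End-points (outcome definitions).** End-points 1 and 2 are the length of the first spell, "defined as the number of calendar days during a continuous episode of full-time or part-time sick leave", cut at 90 and 180 days. The closing rule is that "the end of the first sick leave spell will be censored at 'full sustainable return to work' or end of follow-up", and full sustainable return to work means "having returned to work for 4 weeks or more without benefits". No benefit is named and no exception is made for people already receiving one. End-point 3 counts only new or increased WAA/DP.
- **Source population.** Participants must be "On sick leave for at least 50% of their contracted work hours for 4-12 consecutive weeks". Existing WAA or DP is not an exclusion.
- **Table 2.** One predictor is "Receiving work assessment allowance or disability pension at starting-point", so such people are expected in the sample.
- **Sickness absence data.** WAA and DP can be granted for 20-100% of ordinary hours, and "a person receiving disability pension can also be on part-time sick leave". On counting, "Days on sick leave will be adjusted for part-time sick leave, work assessment allowance, and disability pension", with a further adjustment for contracted hours. Also, "Any new episode or increase in disability pension during follow-up will be counted as sick leave"; that sentence does not mention WAA.

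**The concern.** A person with a stable partial pension who goes back to all contracted hours has returned to work in any ordinary sense, but still receives a benefit. The closing rule then leaves the spell open until the benefit stops or follow-up ends. If every day of that open spell counts, the person is an event on both end-points because of the pension and not because of sick leave.

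The same benefit record also supplies a predictor. If all recipients were coded 1, the coefficient for baseline WAA/DP would be subject to separation in the planned logistic regression. The full-model approach keeps the predictor in regardless, and a uniform shrinkage factor does not repair an infinite estimate. Event rates and apparent discrimination would be inflated. External validation would not reveal the fault, because the same definition would build the same link into the validation outcomes.

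**Working it through.** **1. The rules side by side, for a recipient whose benefit is unchanged**

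| Rule | Treatment of the unchanged benefit |
|---|---|
| Closing rule, end-points 1 and 2 | Prevents closure (benefit unspecified) |
| What is counted, end-points 1 and 2 | Sick-leave days only |
| Sickness absence data | Unchanged DP is not among what counts as sick leave; unchanged WAA is not addressed |
| End-point 3 | Not an event |

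The closing rule is the only one that makes an unchanged benefit matter, and nothing states which rule takes precedence.

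**2. One person under two readings.** Assume sick leave ends 30 days after baseline, all contracted hours are resumed and DP is unchanged.

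- Reading A (spell stays open and every day counts): 365 days, coded 1 on both end-points.
- Reading B (only sick-leave days count): 30 days from baseline. From the start of sick leave, with 4-12 weeks already elapsed, it is 30 + 28 = 58 to 30 + 84 = 114 days. That is coded 0 for >180. For >90 it depends on the time origin, which the end-point section does not state.

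**3. Effect of the contracted-hours adjustment.** The SAP's example is 7 x 0.5 x 1.0 = 3.5 days per week for a 50% worker fully on sick leave.

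- Once the person in step 2 is back in a 50% job the sick-leave grade is 0, so 7 x 0.5 x 0 = 0 days per week accrue, even with the spell nominally open.
- Even if someone were 100% on sick leave for all 365 days, the adjusted count is 365 x contract fraction: 80% gives 292, 50% gives 182.5, 40% gives 146 (not >180) and 20% gives 73 (neither). The contract must exceed 180/365 = 49.3% to pass 180 days and 90/365 = 24.7% to pass 90.

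**4. What remains if the adjusted count governs.** The closing rule still decides what belongs to the first spell. As an illustration with assumed lengths, take an 80% contract, a 20% unchanged pension, and two 60-day periods of full sick leave separated by more than 4 weeks at full contracted hours. The first period alone gives 60 x 0.8 = 48 days, coded 0 for >90. If the spell never closed, the two merge to 120 x 0.8 = 96 days, coded 1.

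**5. Size under reading A.** The number of baseline recipients is not given, so shares of 2%, 5% and 10% of 934 are assumed (19, 47 and 93 people). The section on sample size for development gives 416 and 161 events. 161/934 = 0.172, as printed. 416/934 = 0.445, not the printed 0.403; 0.445 is used here.

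False events = 934 x share x (1 - overall rate), if all recipients are coded 1 and their true rates equal the overall rates.

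| Share | >90 days (x 0.555) | >180 days (x 0.828) |
|---|---|---|
| 2% | 10 | 15 |
| 5% | 26 | 39 |
| 10% | 52 | 77 |

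**The case against.** The strongest reply is that the outcome counts sick-leave days, not benefit days. Someone back in all contracted hours has no sick leave left to count, and the end-point section does not say that later days are added until the spell closes. The section on sickness absence data implies that an unchanged pension contributes nothing. Sensitivity analysis 3, which removes the adjustment for grading and contracted hours, implies that the primary count is adjusted. The return-to-work definition also rests on cited sources not available here, which may limit the benefits meant. Nothing shows that the quoted event counts came from the literal rule.

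Much of this stands. A reader might infer that anyone on WAA or DP at baseline can never close the spell, is always coded >90 and >180, and gives an infinite odds ratio. The documents do not support that:

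- A benefit can stop during follow-up. The SAP's definition of terms describes WAA as support for people expected back at work in the near future.
- The coding follows only if the literal closing rule and an unadjusted day count both apply.
- Complete separation needs every recipient to be an event; one coded 0 removes it.

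The reply does not clear the plan. The sentence on new or increased benefit leaves out WAA, which is half of the predictor. The WAA/DP adjustment has no formula. The end-point section speaks of calendar days, which the definition of terms takes as every day on the calendar, while the other section prorates them. None of this changes the rule that closes the spell.

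**Conclusion.** The point holds as an unresolved conflict in the outcome definition for two of the three models. As written, a person whose baseline WAA/DP continues unchanged cannot close the first spell while it lasts, even at full contracted hours. This contradicts how the SAP counts disability pension elsewhere, and two analysts could code the same person as 365 days or 30.

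The size depends on the reading. With the literal closing rule and every open day counted, the baseline WAA/DP predictor is tied to the outcome by construction and separation is possible. On the assumptions in the working, the upper bound is then about 10, 26 or 52 false events of 416 for >90 days, and about 15, 39 or 77 of 161 for >180 days. The recipient shares are assumed, and taking recipients' true rates as equal to the overall rates is also an assumption. If the adjusted day count governs, the bias is smaller and arises mainly from later sick leave merged into a first spell that never closed. The documents do not show which reading produced the quoted counts.

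**What to change.** - Define full sustainable return to work as at least 4 weeks at work with no sick-leave benefit and no WAA/DP above the person's baseline level. This brings end-points 1 and 2 into line with end-point 3.
- State whether the 90- and 180-day counts use calendar days of the spell or the adjusted days, and whether the treatment of unchanged DP applies equally to WAA.
- Cross-tabulate baseline WAA/DP status against end-points 1 and 2 before fitting, to show whether separation is a real problem.
- Check the event counts in the sample size section under this rule and restate them if they change.
- Apply the same rule in the validation sample.

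The cost is a sentence or two in the SAP and a re-run of the outcome derivation from the registry data the study already uses. No new data collection is needed.
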